7. SAFETY ASSESSMENTS

Participant safety will be monitored once an individual is enrolled in the study. Since our institutional IRB has deemed our TARA intervention to be very minimal risk, we do not anticipate any significant adverse experiences from our TARA intervention. However, to assure comprehensive review of potential safety events, we have included the following alphabetical list of expected adverse experiences for the TARA study intervention, criteria for management and modification of the TARA study intervention regimen or participant assessments if an adverse event occurs:

- 1. Experiencing difficult emotions such as sadness or anger during some of the TARA intervention class activities or home assignments. If participants experience difficult emotions, they can stop the activity and speak to the class leader or study staff. The class leader will talk about how to handle difficult emotions that come up during home assignments at the first class, and throughout the course as needed.
- 2. Restlessness. If participants experience restlessness, they can stop the activity and speak to the class leader or study staff. The class leader will talk about how to handle restlessness that come up during home assignments at the first class, and throughout the course as needed.

If an adverse event occurs, the AE will be assessed by [name] (medical director and co-PI) and recorded in the Adverse Event form (please see Adverse Event form in the Appendix).

7.1 Specification of Safety Parameters

To demonstrate the safety of the TARA intervention, we will carefully record all adverse events and require that < 15% of the participants experience a grade 2 (moderate) or grade 3 (severe) adverse event related to the TARA intervention.

7.2 Methods and Timing for Assessing, Recording, and Analyzing Safety Parameters

The risk profile of our study intervention (TARA) is very minimal. Our institutional IRB has deemed our TARA study intervention to be very minimal risk. Our published peer-reviewed paper using our TARA study intervention in depressed adolescents also demonstrates the exceptional safety and very minimal risk of our TARA study intervention (Henje [name] et al., 2017). The Methods and Timing for Assessing, Recording, and Analyzing Safety Parameters are as follows: (1) At each of the 12 study TARA intervention visits (i.e., TARA visits 1 through 12 [Study visits 2 to 13] as detailed above in section 6.1: Schedule of Evaluations), any and all adverse events will be collected and recorded using the Adverse Event form. Any Adverse Event(s) will be reviewed by the PIs and a determination of the relationship of the Adverse Event to the TARA study intervention will be made by the medical PI ([name]). Based on the study intervention relationship to the Adverse Event as determined by [name] and the severity of the Adverse Event, [name] and [name] will decide upon the appropriate action to take regarding the study intervention (TARA).

If the Adverse Event is classified as Serious Adverse Events, the Serious Adverse Event form will be filled out.

7.3 Adverse Events and Serious Adverse Events

In the present study, an adverse event and serious adverse event will be defined as follows:

An adverse event (AE) will be defined as any unfavorable and unintended diagnosis, symptom, sign (including an abnormal laboratory finding), syndrome or disease which either occurs during the study, having been absent at baseline, or if present at baseline, appears to worsen. Adverse events will be recorded regardless of their relationship to the study intervention.

A **serious adverse event (SAE)** will be defined as any untoward medical occurrence that results in death, is life threatening, requires inpatient hospitalization or prolongation of existing hospitalization, results in persistent or significant disability/incapacity, or is a congenital anomaly.

Since we do not anticipate any laboratory value changes due to the TARA study intervention, no laboratory values will be collected as part of the current protocol; thus, no laboratory values will be collected to assess safety.

Solicited adverse events will be captured in the following manner: (1) the Child Outcome Rating Scale (CORS) including the following question: "Has there been any significant unfavorable change in your mental or physical health since last class?" will be administered at every TARA session (please see Appendix. Not a source document.); (2) if the participant answers "no" to this question on the CORS, then no additional information will be requested; (3) if the participant answers "yes" to this question on the CORS and the reported event meets the definition of an adverse event given above, then the research assistant or another study staff member will ask the participant for additional details regarding the participant's answer to the CORS question and this information will be recorded in the Adverse Event form within 24 hours of the TARA study intervention session.

In order to assure that the reporting and data collection systems avoid double capture of solicited and unsolicited events, we have implemented the following items in our protocol: (1) We will ask all of the participants to report any unsolicited events in the CORS after the question, "Has there been any significant unfavorable change in your mental or physical health since the last class?"; (2) If a participant reports an unsolicited event to any of the study staff, the study staff member will ask the participant to write down this information in the CORS in order to avoid double capture of the event; (3) We also will specifically instruct our research assistants and staff to not duplicate the recording (i.e., double capture) of the same solicited and unsolicited events; (4) At the weekly clinical trial research lab meetings, the PIs (Drs. [name] and [name]) will review with the research staff all of the CORS forms, AE and SAE forms for the prior week in order to ensure that there is no double capture(s) of any solicited and unsolicited event(s).

Time Period and Frequency for Event Assessment and Follow-Up

Unanticipated problems will be recorded in the data collection system throughout the study.

To satisfy the requirement for prompt reporting, unanticipated problems will be reported using the following timeline:

- Unanticipated problems that are serious adverse events will be reported to the IRB, Independent Safety Monitors, and NCCIH within 7 days of the investigator becoming aware of the event.
- Any other unanticipated problem will be reported to the IRB, Independent Safety Monitors, and NCCIH within 15 days of the investigator becoming aware of the problem.

All unanticipated problems will be reported to appropriate institutional officials (as required by an institution's written reporting procedures), the supporting agency head (or designee), and OHRP within one month of the IRB's receipt of the report of the problem from the investigator.

Adverse Event Reporting

SAEs that are unanticipated, serious, and possibly related to the study intervention will be reported to the Independent Safety Monitors, IRB, and NCCIH in accordance with requirements.

- Unexpected fatal or life-threatening AEs related to the intervention will be reported to the NCCIH Program Officer, and Independent Safety Monitors within 7 days of the investigator becoming aware of the event. Other serious and unexpected AEs related to the intervention will be reported within 15 days.
- Anticipated or unrelated SAEs will be handled in a less urgent manner but will be reported to the Independent Safety Monitors, IRB, and other oversight organizations in accordance with their requirements. and will be reported to NCCIH on an annual basis.
- All other AEs documented during the course of the trial will be reported to NCCIH on an annual basis by way of inclusion in the annual report and in the annual AE summary which will be provided to NCCIH and to the Independent Monitors. The Independent Safety Monitors Report will state that all AEs have been reviewed.

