7.4 Reporting Procedures

Please see below, Table A, for details of the reporting procedures and timelines, including the individual responsible for each step (e.g., the PIs, the Independent Monitors, etc.). The medical director, [name] (co-PI), will make the decision regarding determining the relatedness and severity of any and all AEs and SAEs. The appropriate AE and SAE forms will be completed. The completed AE and SAE forms will be sent and distributed to the appropriate individual or group of individuals (i.e.,

UCSF IRB, NCCIH) as stated below in Table A (please see below, Table A). The PIs will record all reportable events with start dates occurring any time after informed consent is obtained until 7 days (for non-serious AEs) or 30 days (for SAEs) after the last day of study participation. A research assistant will perform the duties of the Internal QA reviewer. At each study visit, the investigator will inquire about the occurrence of AE/SAEs since the last visit. Events will be *followed* for outcome information until resolution or stabilization.

Table A

Data type	Frequency of review	Reviewer
Subject accrual (including compliance with protocol	Monthly	PIs, Internal QA Reviewer
enrollment criteria)	Semi-annually	Independent Monitors
Status of all enrolled subjects, as	Monthly	PIs, Internal QA Reviewer
of date of reporting	Semi-annually	Independent Monitors
Data entry quality control checks on 100% of charts	Weekly	QA Reviewer
Adherence data regarding study	Monthly	PIs, Internal QA Reviewer
visits and intervention	Semi-annually	Independent Monitors
AEs and rates (including out-of-	Monthly	PIs, Internal QA Reviewer
range lab values)	Semi-annually	Independent Monitors
	Annually	NCCIH
SAEs (unexpected and related)	Per occurrence	PIs, Independent Monitors NIH/NCCIH
SAEs (expected or unrelated)	Per Occurrence	PIs, Internal QA Reviewer
	Annually	Independent Monitors, NIH/NCCIH
Unanticipated Problems	Monthly	PIs, Internal QA Reviewer
	Per Policy	IRB

Reporting Changes in Study Status

During the funding of this study, any action by an IRB, the Independent Monitors, or one of the study investigators that results in a temporary or permanent suspension of the study will be reported to the NCCIH Program Official within 3 business days of notification.

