7.5 Followup for Adverse Events

The PIs will record all reportable events with start dates occurring any time after informed consent is obtained until 7 days (for non-serious AEs) or 30 days (for SAEs) after the last day of study participation. At each study visit, the investigator will inquire about the occurrence of AE/SAEs since the last visit. Events will be followed for outcome information until resolution or stabilization. In the cases of adolescents with severe depression or adolescents expressing passive suicidal ideation (i.e., the adolescent expresses some potential thoughts of self-harm, but there is no intent or plan to harm herself/himself), study participants with commercial or private health insurance plans will be referred to the UCSF Langley Porter Psychiatric Institute where [name] (co-PI) sees patients, and study participants without commercial or private insurance will be referred to the UCSF Zuckerberg San Francisco General Hospital which cares for all patients regardless of their ability to pay. Participants expressing imminent suicidal ideation will be placed on an involuntary 5150 72-hour hold for danger to self by [name]. [name] is a double board certified adult as well as child and adolescent psychiatrist who sees patients at UCSF, and he is legally authorized to place an involuntary 5150 72-hour hold on the adolescent for danger to self (i.e., suicidal ideation) in order to hospitalize the adolescent if needed. The UCSF Emergency Room (ER) is located immediately adjacent to the UCSF Langley Porter Psychiatric Institute where [name] personal clinical office and research lab are located. Following the established written protocols that are currently in place for any adolescent who expresses imminent suicidal ideation, [name] would evaluate and place an involuntary 5150 72-hour hold for danger to self on the suicidal adolescent. [name] would then contact the UCSF Langley Porter Psychiatric Institute security who are present in the building throughout the entire day and evening to help escort the suicidal adolescent to the UCSF ER. The ER physician in consultation with the on call child and adolescent psychiatrist would then evaluate the patient in the ER and decide whether to hospitalize the patient for the adolescent's safety and well-being.

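### The SAE list has no criterion for an important event without admission, so a psychiatric hold released from the ER can be classed as non-serious and reach the monitors months later

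*Combined protocol and SAP*

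**What the plan says.** Section 7.3 defines an SAE by a list that opens with death and a threat to life and closes with an event that "requires inpatient hospitalization or prolongation of existing hospitalization, results in persistent or significant disability/incapacity, or is a congenital anomaly". There is no criterion based on medical judgement. Suicidality, involuntary holds and emergency care are not mentioned.

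Section 7.5 describes what happens when a participant is acutely suicidal: "Participants expressing imminent suicidal ideation will be placed on an involuntary 5150 72-hour hold for danger to self". The participant is escorted to the ER, where the ER physician, with the on-call psychiatrist, "would then evaluate the patient in the ER and decide whether to hospitalize the patient". Hold and admission are thus two steps, and the second need not follow from the first.

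For events that are not serious, Section 7.3 (Adverse Event Reporting) says: "All other AEs documented during the course of the trial will be reported to NCCIH on an annual basis", by way of the annual report and an "annual AE summary which will be provided to NCCIH and to the Independent Monitors". Table A, printed in Sections 7.4 and 10.3.5, instead puts adverse events before the monitors semi-annually. Section 7.3 also has a 15-day report to the IRB, the monitors and NCCIH for an unanticipated problem that is not an SAE. Table A's row for unanticipated problems names the PIs, the internal QA reviewer and the IRB, but not the monitors.

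**The concern.** The protocol plans for a specific severe event and then leaves its seriousness to depend on what the ER decides. Two participants with the same behaviour and the same hold could be classified differently, one because a bed was given and the other because it was not.

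What is at stake is prompt independent review. Participants are aged 14 to 18, the intervention works on emotional health, and Section 5.2 uses suicidal ideation as its own example of a safety concern. Section 9.4 describes the trial as preliminary to a decision on a study in depressed adolescents. Monitors of such a trial would expect to hear of a hold soon after it happens. As written, whether they do depends on judgements made within the study team.

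**Working it through.** No stated figure has to be reproduced. The check follows one event through the text: a participant is placed on a hold, taken to the ER and released.

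**Step 1: is it an SAE under Section 7.3?** Death, disability and congenital anomaly do not apply. Inpatient hospitalization is not met, because Section 7.5 treats admission as a later and separate decision. That leaves the life-threatening criterion, which is a judgement. If the event is not judged life threatening, it meets no item on the list. A suicidal act follows the same path, although the life-threatening criterion is more likely to be met.

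**Step 2: when do the monitors hear of it?**

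| Classification of the event | Route to the Independent Monitors | Source |
|---|---|---|
| Non-serious AE | Semi-annually | Table A |
| Non-serious AE | Annual summary | Section 7.3 |
| Unanticipated problem, not an SAE | 15 days | Section 7.3 |
| Unanticipated problem | Monitors not listed | Table A |
| Life threatening, unexpected, related | 7 days | Section 7.3 |
| Other SAE, unexpected and related | 15 days; per occurrence | Section 7.3; Table A |
| SAE, expected or unrelated | Annually | Table A |

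The first two rows disagree with each other, as do the third and fourth. The last row is slower than the first: under Table A, an SAE judged unrelated has a less frequent scheduled monitor review than an ordinary AE.

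**Step 3: size of the delay.**
- Semi-annual interval: 26 weeks × 7 = 182 days, the longest wait if the event falls just after a review. Against the 15-day limit, 182 / 15 ≈ 12 times as long.
- Annual summary: up to about 12 months.
- Maximum follow-up of one participant (Section 3): 20 weeks. Since 26 > 20, the monitors could learn of the event after that participant has left the study.

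**Step 4: is there an aggregate backstop?** The safety review in Section 9.4 is triggered at 15% of enrolled participants with a related grade 2 or 3 event. With 100 enrolled, 0.15 × 100 = 15 participants. A single event cannot trigger it.

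**The case against.** A reader might infer that the definition turns on admission alone, so that any suicidal act released from the ER is automatically non-serious. The text does not support that. A threat to life is an independent criterion, and a suicidal act can be an SAE whatever the ER decides. The hold without admission is the clearer example, and the right statement is that the event *can be* classed as non-serious.

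The 15-day route for unanticipated problems is a fair answer as far as it goes. It requires no seriousness. A suicidal event could well be called unanticipated: Section 7 lists only difficult emotions and restlessness as expected, and Section 4.2 excludes suicidal ideation or attempt in the past 3 months. But the protocol does not define the term, and Table A leaves the monitors out. The route narrows the gap without closing it.

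A reader might also infer that widening the definition would by itself bring reporting within 7 to 15 days. It would not. Those limits for SAEs apply to unexpected and related events, or to those declared unanticipated problems. Relatedness is decided by the medical director, who is a co-PI (Section 7.4). The relatedness and expectedness rules contribute to the delay as well as the definition.

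Nor would the event vanish from the analysis. Section 9.6 compares adverse events of grade 2 or higher between arms without regard to seriousness or relatedness, so it would be counted if graded 2 or higher. The Go/No-Go criteria in Section 1.1 are effect size and retention, so no stated decision rule depends on seriousness.

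Other oversight exists. The PIs review all CORS, AE and SAE forms weekly (Section 7.3), and an unblinded research assistant gives the monitors case-by-case reports (Section 6.2.3). The first is not independent; the second has no stated trigger or deadline. The SAE form and the data and safety monitoring plan were not available and may already say more.

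**Conclusion.** The gap is real and moderate in size. A hold, or a suicidal act not judged life threatening, that ends with release from the ER can be classed as non-serious. Unless it is declared an unanticipated problem, the only dated routes by which the monitors receive it are at about 6 or about 12 months, depending on which of two conflicting statements is followed.

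This rests on three assumptions: that the event is not judged life threatening, that a hold in the ER is not itself treated as inpatient hospitalization (Section 7.3 does not say, and Section 7.5 separates the two), and that the unseen SAE form and monitoring plan add no further criterion or deadline. The number of such events is unknown and probably small in a sample screened as healthy. No efficacy estimate is affected. The change is still worth making, because the protocol foresees the event in minors and gives it no dependable prompt route to independent review.

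**What to change.** 1. Add an important-medical-event criterion to the SAE definition in Section 7.3, and to the SAE form if it lacks one, for example: *or is an important medical event that may need intervention to prevent one of these outcomes, including any suicide attempt or involuntary psychiatric hold, whether or not the participant is admitted.*
2. State in Section 7.3 and Table A that these events are notified to the Independent Monitors per occurrence, regardless of relatedness or expectedness. Without this, one judged unrelated or expected would move to Table A's annual row.
3. Define unanticipated problem, and reconcile Section 7.3 with both printings of Table A (Sections 7.4 and 10.3.5) on two points: whether the monitors receive unanticipated problems, and whether adverse events reach them semi-annually or annually.

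The cost is a few sentences, a table correction, and possibly a few more expedited reports. Only classification and reporting change; the clinical handling described in Section 7.5 stays as it is.

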6.2 Description of Evaluations

6.2.1 Screening Evaluation

These evaluations occur to determine if the candidate is eligible for the study.

Definitions of the column headings in the Schedule of Evaluations (Section 6.1): (1) Assessment refers to the specific assessments as listed in the first column that will be performed at each of the study visits; (2) Visit 1 (Day 0) refers to all of the assessments that will occur at the first study visit; (3) Visits 2 to 13 refer to the assessments that will occur at each of the study visits 2 through 13 which correspond to the TARA study intervention sessions 1 through 12 (i.e., Study Visit 2 is TARA study intervention session 1 since the first TARA study intervention session will take place on Study Visit 2); (4) Final Visit 14 refers to all of the assessments that will occur on the final study visit which will be Visit 14. Please note that in the above Schedule of Evaluations (Section 6.1), the AE and SAE forms only will be completed if an AE and/or SAE are reported by a participant. In addition, if a participant prematurely leaves the study, all of the assessments listed under the final study visit 14 column will be performed.

A phone pre-screening evaluation will occur to determine if the candidate adolescent is eligible for the study prior to the initial visit, and a screening evaluation will occur at Visit 1 (Day 0) to determine if the candidate is eligible to enter the study.

Consenting Procedure

A trained research staff member who will have at least a college degree (i.e., Bachelor's degree or higher) will perform the following informed consent process.

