6.2.4 Followup Visits

The following study visits must be performed on the weeks indicated above in the Schedule of Evaluations (please see Section 6.1) plus/minus 5 (five) *working* days (i.e., Monday through Friday, not including weekends and holidays):

- Visit 1:
 - Informed Consent Form
 - Medical History Form
 - Inclusion/Exclusion criteria form
 - Enrollment/Randomization form
 - MRI Screening Form & urine pregnancy test
 - MRI brain scan
 - Demographics assessment (electronically in Qualtrics)
 - SDQ assessment (electronically in Qualtrics)
 - Baseline Checklist
- Visit 2 through Visit 13:
 - Child Session Rating Scale (CSRS)
 - Child Outcome Rating Scale (CORS) including the question: "Has there been any significant unfavorable change in your mental or physical health since last class?" (please see Appendix. Not a source document.)
 - Adverse Events (if answered Yes the question above in CORS)
 - Serious Adverse Events (if answered Yes to the SAE question in the Adverse Event form)
 - On Study Visit Checklist Form (modified to include Treatment Administration information)

6.2.5 Completion/Final Evaluation.

The following assessments will be performed at the participant's final visit (Visit 14):

- SDQ assessment (electronically in Qualtrics)
- MRI Screening Form & urine pregnancy test
- MRI brain scan
- Child Outcome Rating Scale (CORS) including the question: "Has there been any significant unfavorable change in your mental or physical health since last class?" (please see Appendix. Not a source document.)
- Adverse Events (if answered Yes the question above in CORS)
- Serious Adverse Events (if answered Yes to the SAE question in the Adverse Event form)
- Study Completion form.

For study participants who discontinue the study intervention early, all of the following assessments will be performed:

- SDQ assessment (electronically in Qualtrics)
- MRI Screening Form & urine pregnancy test
- MRI brain scan
- Child Outcome Rating Scale (CORS) including the following question: "Has there been any significant unfavorable change in your mental or physical health since last class?" (please see Appendix. Not a source document.)
- Adverse Events (if answered Yes the questions above in CORS)
- Serious Adverse Events (if answered Yes to the SAE question in the Adverse Event form)
- Study Completion form.

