10. DATA COLLECTION AND QUALITY ASSURANCE

10.1 Data Collection Forms

Information for each participant will be collected using the following forms and procedures:

- o Informed Consent Form (will be obtained and signed by RA via DocuSign)
- Medical History Form (source document, will be collected and signed by RA via DocuSign)
- o Inclusion/Exclusion criteria form (source document, will be filled out and signed by RA via DocuSign)
- Enrollment/Randomization form (source document, will be filled out and signed by RA via DocuSign)
- o MRI screening form (will be signed by the MRI technician. Not a source document.)
- o MRI brain scan (will be performed using a 3T MRI scanner)
- o Demographics assessment (will be performed electronically in Qualtrics)
- SDQ assessment (will be performed electronically in Qualtrics)
- Baseline Visit Checklist (source document, will be filled out and signed by RA via DocuSign)
- Child Session Rating Scale (CSRS) (source document, will be collected and signed by RA)
- Child Outcome Rating Scale (CORS) including the question: "Has there been any significant unfavorable change in your mental or physical health since last class?" (will be collected by RA. Not a source document.)
- o Adverse Events (source document, if the answer is Yes to the question above in CORS, this form will be filled out and signed by RA via DocuSign)
- Serious Adverse Events (source document, if answered Yes to the SAE question in the Adverse Event form, this form will be filled out by RA, signed by PI via DocuSign)
- o On Study Visit Checklist Form (source document, will be filled out and signed by RA via DocuSign)
- Study Completion form (source document, will be filled out by RA, signed by PI via DocuSign).

All source documents will be signed and stored electronically in DocuSign. Any data, forms, reports, video recordings, and other records that leave the site will be identified only by a participant identification number (Participant ID, PID) to maintain confidentiality. All computer entry and networking programs will be done

using PIDs only. Information will not be released without written permission of the participant, except as necessary for monitoring by the UCSF IRB, the NCCIH, and the OHRP.

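### Section 7.3 applies the adverse event definition before details are gathered, while 6.2.4, 6.2.5 and 10.1 complete the form for every CORS 'yes'; the triggers need reconciling

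*Combined protocol and SAP*

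**What the plan says.** Section 7.3 describes the procedure at TARA sessions. Participants answer a CORS question on whether their health has changed for the worse since the last class. A 'no' ends the matter. A 'yes' goes forward only if a second condition is met: "the reported event meets the definition of an adverse event given above, then the research assistant or another study staff member will ask" for additional details. After that, "this information will be recorded in the Adverse Event form within 24 hours of the TARA study intervention session".

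Other sections set the trigger differently. For Visits 2 to 13, Section 6.2.4 lists "Adverse Events (if answered Yes the question above in CORS"), with no further condition. Section 6.2.5 does the same for the final visit and for early discontinuation. Section 10.1 says that "if the answer is Yes to the question above in CORS, this form will be filled out and signed by RA via DocuSign". Section 6.2.1 has another wording: "the AE and SAE forms only will be completed if an AE and/or SAE are reported by a participant".

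On who judges, Section 7.4 says that the medical director, who is a co-principal investigator, "will make the decision regarding determining the relatedness and severity of any and all AEs and SAEs". Section 7.3 also has a weekly meeting at which the principal investigators "will review with the research staff all of the CORS forms, AE and SAE forms for the prior week", with the stated aim of preventing double capture. Sections 7.4 and 7.5 have the investigator ask about adverse events at each study visit.

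**The concern.** The definition in 7.3 turns on whether something is new since baseline or has worsened. A 'yes', even with a short note beside it, will often not settle that, and the follow-up questions are what would. Section 7.3 puts the judgement ahead of those questions and does not say who makes it. The natural reading is the research assistant or other staff member, because they act next, but the text only implies this.

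Staff cannot follow all the sections at once. One who follows 6.2.4 or 10.1 completes a form for every 'yes'. One who follows 7.3 completes a form for some of them, and nothing requires the rest to be explained.

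Adverse event counts feed three things: the safety criterion in 7.1 and 9.5.2 (fewer than 15% of participants with a related grade 2 or 3 event), the safety review trigger in 9.4, and the between-arm tabulation and Fisher exact test in 9.6. Incomplete capture, or capture that varies with the section a staff member works from, would carry into all three.

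**Working it through.** The plan states no figure on this point, so the check is a comparison of the sections.

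**1. What triggers the Adverse Event form**

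| Section | Condition for completing the form |
|---|---|
| 7.3 | CORS 'yes' and the event already judged to meet the definition |
| 6.2.4 (Visits 2 to 13) | CORS 'yes' |
| 6.2.5 (Visit 14, early discontinuation) | CORS 'yes' |
| 10.1 | CORS 'yes' |
| 6.2.1 | Participant reports an adverse event or serious adverse event |

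The 6.2.1 wording fits either rule, depending on whether a 'yes' counts as reporting an event. It does not settle the conflict.

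**2. The order of steps in 7.3.** The sequence is: a 'yes', then the definition, then a request for details, then the form within 24 hours. The judgement comes before the request for details.

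**3. What happens to a 'yes' judged not to qualify under 7.3**

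- No follow-up questions are asked, because asking depends on the judgement.
- No Adverse Event form is completed, because the form records the answers.
- The serious adverse event question is not reached. Sections 6.2.4, 6.2.5 and 10.1 place it on the Adverse Event form, and the serious event form depends on its answer.
- What remains is the CORS. Sections 6.2.4, 6.2.5, 7.3 and 10.1 all mark it as not being source, whereas 10.1 lists the Adverse Event form as source.

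**4. Who can still pick it up**

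- *Weekly meeting (7.3).* All CORS forms are reviewed, not only those that led to an Adverse Event form, and the medical director attends as a co-principal investigator. The stated purpose is double capture. Finding a 'yes' with no form is not mentioned, and a weekly meeting can fall days after the 24-hour recording window.
- *Written entries on the CORS (7.3).* Participants are asked to write unsolicited events there, so some description may exist.
- *Investigator inquiry at each visit (7.4, 7.5).* This is a separate route. The body of the document gives no question or form for it apart from the CORS item. The forms in the appendix are not available to this review.

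**5. Size.** No section gives the number of 'yes' answers expected or the share that would be judged not to qualify, so no effect can be computed. Only the position of the 15% line follows from the documents, and it depends on the denominator:

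- With the 50 planned TARA participants, 0.15 × 50 = 7.5. The criterion passes at 7 (7/50 = 14%) and fails at 8 (8/50 = 16%).
- With the 100 planned participants, 0.15 × 100 = 15. The criterion passes at 14 and fails at 15. Section 9.4 refers to enrolled participants, so its review trigger also falls at 15.

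These counts locate the line. They do not say how far capture would move the result.

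**The case against.** The case on the other side is substantial. A reader might infer that 7.3 hides events from the medical director. The documents do not support that: the director is one of those who review all CORS forms each week, and the investigator also asks about events at each visit. A reader might also infer that the judgement rests on a bare yes or no. Section 7.3 speaks of a reported event and of additional details, and it asks participants to write unsolicited events on the CORS, so some description may already be there.

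The filter may also be thin. The definition covers almost any unfavorable new or worsened symptom, whatever its cause, and the CORS asks only about changes of some significance, so few 'yes' answers should fail it. Section 7 lists difficult emotions and restlessness as expected adverse experiences, which tells staff that they count. Section 7.2 requires all adverse events to be collected and recorded. The entries in 6.2.4 and 10.1 are lists, and it can be argued that 7.3 is the operative procedure. Finally, a form that is not source is not thereby discarded.

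Most of this stands, and it limits the harm. It does not remove the conflict. If the two triggers nearly coincide, little is lost by dropping the extra condition. If they do not coincide, the only routine check on the difference has a different stated purpose.

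**Conclusion.** The conflict is real: 7.3 requires a prior judgement that 6.2.4, 6.2.5 and 10.1 do not. It asks for that judgement before the details that would inform it, and does not name who makes it. An event answered 'yes' but judged not to qualify can go without follow-up questions, an Adverse Event form and the serious event question, unless the weekly review or the investigator's inquiry happens to catch it.

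The size cannot be stated. A reader might build an example in which a few lost reports turn a failed safety criterion into a passed one. Any such example needs an event rate and a loss rate that the documents do not give. It also needs a choice of denominator: one based on 50 TARA participants does not carry over to the 9.4 trigger, which refers to enrolled participants.

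Two readings underlie this conclusion: that 7.3 is meant to be followed as written, and that the appendix forms contain no instruction that resolves the difference. It is a modest point, worth correcting because the correction is nearly free and improves capture of both adverse and serious adverse events.

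**What to change.** - In 7.3, delete the condition that the event must already meet the definition. Every 'yes' then leads to details on the Adverse Event form within the existing 24 hours, as 6.2.4, 6.2.5 and 10.1 already imply.
- Apply the definition afterwards, at the existing review by the principal investigators. Where the decision is that the report is not an adverse event, note that on the form.
- Extend the stated purpose of the weekly CORS review to include a check for 'yes' answers without an Adverse Event form.
- Bring the wording of 6.2.1 into line with the same trigger.

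The cost is a few sentences of text and a few more forms for minor complaints. No new visit, instrument or staff member is needed.
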